10.2 Lost to follow up

How participants will be identified as lost to follow-up: A participant will be deemed lost to follow-up if they stop attending all scheduled trial visits without a loco-regional recurrence event being reported, in the absence of a withdrawal form indicating complete withdrawal from the trial.

Measures that we will take to try and get the missing info: If there is no evidence the patient has lost capacity. The site can continue to attempt to contact the patient or access their medical records while the trial is still open. Visits will be marked as not done on the trial database stating the reason as "patient did not attend".

Which outcome data will be collected from protocol non-adherers: Medical records of any skin examinations, CT scans or death data.

11 Trial Intervention

11.1 Radiotherapy Treatment

Radiotherapy should be delivered to the skin with electrons. Alternative radiotherapy techniques would be permitted but should be discussed with the SCC-After trials team. The radiotherapy dose

and fractionation are dependent on the size of the treatment field. The permitted radiotherapy dose and fractionation schedules are:

- Field diameter less than 8cm: 45Gy in 10 daily fractions over 2 weeks or 55Gy in 20 daily fractions over 4 weeks
- Field diameter 8cm or greater: 55Gy in 20 daily fractions over 4 weeks or 60Gy in 30 daily fractions over 6 weeks

Field diameter above is with reference to an 8cm circular radiotherapy field.

Fractionation (total dose, number of fractions, dose per fraction) Treatment once a day, Mon to Fri)	EQD2 for tumour α/β -ratio 10Gy	EQD2 for normal tissues (e.g. bone) α/β -ratio 3Gy
45Gy/10F/4.5Gy	54.38*	67.5**
55Gy/20F/2.75Gy	58.44	63.25
60Gy/30F/2Gy	60	60

*Shorter treatment time giving greater tumour radiobiological equivalence

**Smaller field size abrogating higher risk to normal tissue (bone)

EQD₂ calculator: <https://www.mdcalc.com/calc/10111/radiation-biologically-effective-dose-bed-calculator>

Detailed radiotherapy guidelines are provided in a separate document SCC-AFTER Radiotherapy Planning Guidance Document (RPGD). Investigators MUST follow the detailed instructions in the RPGD, which will be distributed by the CTR in conjunction with the National Radiotherapy Trials Quality Assurance (RTTQA) Group.

11.3 Radiotherapy quality assurance

The quality assurance programme for the trial will be co-ordinated by the National RTTQA Group. Participating centres will submit a pre-trial facility questionnaire prior to gaining RTTQA approval.

The details of the QA programme can be found at www.rtrialsqa.org.uk.

11.7 Participant positioning and planning CT scan acquisition

Use of a CT scan in planning is not required. In some instances, clinician decision or local standard of care may indicate it is required and this will be allowed and documented.

There is no funding for sample collection, and it is the intention to request this collection of surgical tissue blocks at a later date when funding has been secured. If funding is not secured the surgical tissue block will remain at the NHS sites in line with NHS retention guidelines and site SOPs.

14 Trial procedures

The schedule of assessments can be found in table 1. A breakdown of the QoL questionnaires and clinician and patient reported toxicity timepoints. All procedures to be carried out by clinical and/or research team at the participating site, according to the site delegation log.

14.1 Screening (baseline) assessments

Randomisation should be within 2 months of surgery. A window up to 3 months post-surgery will be allowed. Where additional time has been needed to heal or for other reasons to be discussed with the SCC-AFTER trial team before the patient is consented.

Patients should undergo the following assessments at the time of trial entry and no more than 2 weeks after randomisation:

- Medical History.
- Physical Examination.
- Height/Weight.
- ECOG performance status.
- Toxicity Assessment.
- QoL Questionnaires (to be completed after trial consent). EQ-5D, EORTC QLQ30, health utilisation.

Toxicity should be assessed according to CTCAE 5.0.

14.2 Pre-treatment assessments; additional to screening assessment for patients randomised to the radiotherapy arm

Patients should undergo the following assessments at the time of trial entry and before treatment with radiotherapy. Radiotherapy should start within one month of randomisation.

- Physical Examination.
- Pregnancy test in people of childbearing potential who are randomised to the Radiotherapy treatment arm.
- Key concomitant medication check.

All baseline assessments and pre-treatment assessments must be completed prior to the start of any radiotherapy treatment.

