16.1 Randomisation

Participants recruited should be randomized to each group with a fixed ratio of 1:1 using a centralized internet randomization. Randomisation will be by minimisation with a random element. Randomisation stratification factors will be; age category, stage of cancer, immunocompromised, time since surgery and perineural invasion. The trial is open-label since participants in the intervention arm will receive radiotherapy.

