17.3 Quality of Life (QoL)

QoL improvement will be assessed primarily using the global health status derived from the EORTC QLQ-C30 questionnaire at 4 months from baseline (change from baseline in global health status score) between the two arms. This will be calculated as per scoring instructions in the EORTC QLQ-C30 manual. For analyses, descriptive statistics will be produced, using medians and interquartile ranges (IQRs) instead of means and standard deviations in cases of heavily skewed data. The standardized Skin Cancer Index questionnaire will be analysed, and missing data handled in accordance with their respective guidelines. Proportion of patients experiencing a change from baseline for each measure as well as mean group changes will be calculated. Associations between the reporting of skin toxicity due to radiotherapy between clinicians and patients (using CTCAE, v5.0) at the same timepoints will be explored. In addition, sub-group analyses based on age, gender, treatment arm, will be undertaken. Statistical significance tests will be carried out if clinically significant differences are observed. Independent samples t-tests will be used to compare means, and the nonparametric equivalent will be used to compare medians in the case of skewed data. Proportions will be compared using the chi-square test. Associations will be explored using multivariate regression analyses if sample size allows.

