17.5 Cost effectiveness analysis

A full Health Economic Analysis Plan will be specified prior to data lock (43). Patient-level cost and utilities will be analysed using regression models to estimate mean costs associated with clinically meaningful health states (e.g., LRR and progression-free survival, progressive disease, toxicity, disease-specific and all-cause death). These states will be the basis of a Markov model to extrapolate

costs and consequences over time. The regression analyses will account for the distributions of costs and utilities and correct for any baseline imbalance in EQ-5D-5L utility scores (44). Parametric functions will be used to model LRR, progression-free and overall survival. Different functional forms will be tested for suitability based on goodness of fit criteria and informed by external data from published sources (45).

A stochastic sensitivity analysis will be carried out to estimate the incremental cost-effectiveness ratio, and to assess the probability of cost-effectiveness for given threshold values of willingness to pay. This will consider simultaneous uncertainty in parameter inputs and provide evidence suitable to decision makers on the cost-effectiveness of ART. Additional sensitivity and scenario analyses, will be undertaken to account insofar as possible, different sources of uncertainty. A stratified cost-effectiveness analysis will be conducted for valid sub-groups that will be specified *a priori*.

18 Data Management

Source Data is defined as “All information in original records and certified copies of original records of clinical findings, observations, or other activities in a clinical trial necessary for the reconstruction and evaluation of the trial. Source data are contained in source documents.” There is only one set of source data at any time for any data element, as defined in site source data agreement.

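### Baseline quality-of-life and EQ-5D forms may be completed up to 2 weeks after open-label randomisation, so the baseline behind the 4-month change score can reflect knowledge of the arm

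*Protocol*

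**What the plan says.** Section 14.1 opens its list of screening (baseline) assessments with: "Patients should undergo the following assessments at the time of trial entry and no more than 2 weeks after randomisation". The list covers medical history, physical examination, height and weight, ECOG, toxicity and the questionnaires. The questionnaire entry reads: "QoL Questionnaires (to be completed after trial consent). EQ-5D, EORTC QLQ30, health utilisation". Table 2 also ticks the Skin Cancer Index (SCI) and both patient- and clinician-reported toxicity at baseline.

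The pre-treatment subsection that follows sets one more limit: "All baseline assessments and pre-treatment assessments must be completed prior to the start of any radiotherapy treatment". It also says: "Radiotherapy should start within one month of randomisation".

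On blinding, section 16.1 says: "The trial is open-label since participants in the intervention arm will receive radiotherapy". Section 9.5.2 has the database confirm the allocated arm as soon as randomisation is complete.

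The baseline score is used in two places. Section 17.3 makes global health status at 4 months the main QoL measure, analysed as "change from baseline in global health status score) between the two arms", with independent-samples t-tests for means. Section 12 makes baseline the first EQ-5D-5L time point, and the regressions in section 17.5 are to "correct for any baseline imbalance in EQ-5D-5L utility scores".

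**The concern.** A baseline is useful in a randomised comparison because allocation cannot have influenced it. Here it can. A patient who has just learned that they will, or will not, have several weeks of radiotherapy may answer questions on worry, tension and overall quality of life differently for that reason alone. Any such shift is a consequence of allocation. Subtracting it from the 4-month score carries it into the between-arm difference with its sign reversed. The utility correction in section 17.5 would treat it as chance imbalance and adjust for it.

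At stake are the main QoL comparison and the utility input to the economic analysis. Both are secondary, but the protocol names effects on QoL and cost-effectiveness among the purposes of the trial.

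**Working it through.** The plan gives no figure on this point to reproduce. The check has two parts.

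**1. Does any passage keep allocation out of the baseline?**

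- Questionnaires must follow consent (14.1). This sets no order relative to randomisation.
- Baseline must precede radiotherapy (pre-treatment subsection). This keeps out an effect of treatment. Radiotherapy may start up to one month after randomisation, so the whole 2-week window can fall after allocation and before treatment.
- Table 1 puts consent, randomisation, toxicity and the questionnaires in one Baseline column, with no order stated.
- Section 9.1 requires consent and confirmation of potential eligibility before randomisation, but says nothing about questionnaires.

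No passage requires the questionnaires before the arm is known.

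**2. What would a shift do?**

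Let a fraction p of one arm complete baseline after allocation, and let knowing the arm move their score by d on average. If both arms shift, replace p × d by the difference between the arms in that product.

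- Change score: bias = −p × d.
- Analysis adjusted for baseline (ANCOVA): bias ≈ −r × p × d, where r is the correlation between baseline and 4 months, taking equal variances.
- 4-month score without the baseline: bias = 0.

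The documents give none of p, d, r or the standard deviation. The following only shows scale. **Assumed**: SD 20 to 25, r 0.4 to 0.6, no true effect, and 420 per arm (840/2, with no losses).

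SE of the change-score difference = SD × √(2(1 − r)) × √(2/420):

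- SD 20, r 0.6: 20 × √0.8 × √(2/420) = 1.23
- SD 25, r 0.4: 25 × √1.2 × √(2/420) = 1.89

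With λ = p × d / SE, the false-positive rate of the two-sided 5% test is Φ(λ − 1.96) + Φ(−λ − 1.96). ANCOVA uses the same formula with bias r × p × d and SE = SD × √(1 − r²) × √(2/420).

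| p × d (points) | Change score: bias, false-positive rate | ANCOVA: bias, false-positive rate |
|---|---|---|
| 0 | 0, 5% | 0, 5% |
| 1 | 1, about 8–13% | 0.4–0.6, about 6–8% |
| 2 | 2, about 19–37% | 0.8–1.2, about 8–19% |

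The 2-point row arises if everyone in one arm is late with d = 2, or half are late with d = 4. If a quarter are late with d = 4, p × d = 1. These rates ignore the condition in section 17.3 that tests are run only when clinically significant differences are seen.

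For utilities, assume an average shift of 0.03 in one arm. The direct effect on the area under the curve, over the roughly 7 weeks to the next form, is 0.5 × (7/52) × 0.03 = 0.002 QALY. A regression correction would move the QALY difference by its coefficient × 0.03, which is 0.015 to 0.06 for assumed coefficients of 0.5 to 2.0. The economic result comes from a lifetime Markov model (sections 12 and 17.5), so these figures cannot be carried through to the cost-effectiveness ratio.

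**The case against.** The strongest reply is practical. Two weeks is an upper limit, and Table 1 groups consent, randomisation and baseline forms together. Many patients may complete them in one sitting before allocation, so p may be small. Forms carry a completion date (section 18.2 and Appendix 1), so late baselines can be found. The objection stands as regards size. It does not remove the permission, and a date cannot show the order of events on the same day.

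A reader might infer more than the documents support:

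- **That eligibility or the primary endpoint is compromised**, because examination and ECOG sit in the same 14.1 list and a recurrence found late could be either ineligibility or an event. Table 1 places medical history, examination and ECOG under Screening, and section 9.1 requires potential eligibility to be confirmed before randomisation. What remains is a conflict of wording between 14.1 and Table 1.
- **That the toxicity comparison is biased.** Sections 5.2 and 5.4 define it by the proportion experiencing toxicity, using CTCAE and serious adverse events. Nothing makes it a change from baseline.
- **That the damage is beyond repair.** Comparing 4-month scores without the baseline is still a randomised comparison, free of this problem. It costs precision: relative to ANCOVA the SE is larger by 1/√(1 − r²), a factor of 1.09 at r = 0.4 and 1.25 at r = 0.6.
- **That a particular bias can be expected.** Any figure in standard errors rests on assumed values and on an assumed share of late forms.
- **That the absence of the SCI from the 14.1 list adds weight.** Table 2 already requires it at baseline, so this is a separate drafting slip.

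**Conclusion.** The point holds for the baseline questionnaires. The protocol permits QLQ-C30 and EQ-5D, and in effect SCI, to be completed with the arm known, and then uses baseline scores in the main QoL contrast and the utility correction. The bias is p × d for a change score and less with baseline adjustment. Its direction and size cannot be derived from the documents. The illustration shows only that, under the stated assumptions, an average one-arm shift of 1 to 2 points would be enough to distort the test. The direct QALY effect would be small, and the effect through the regression depends on its coefficient. The primary analysis, event target and alpha are not affected. The change is worth making because it removes the problem by design at almost no cost.

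**What to change.** - In section 14.1 and Tables 1 and 2, require baseline QLQ-C30, EQ-5D and SCI, and baseline toxicity, after consent and before randomisation. Delete the 2-week post-randomisation allowance for these items and add SCI to the 14.1 list.
- Add an item to the first part of the randomisation eCRF confirming that the baseline forms are complete.
- For any patient whose form is dated after randomisation, plan a sensitivity analysis, for example comparing 4-month scores without the baseline.
- Reconcile 14.1 with Table 1 on medical history, physical examination and ECOG.

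The cost is protocol wording and one eCRF check. Sample size, events and alpha do not change. The small downside is that patients must finish the questionnaires before they can be randomised, which may lengthen the consent visit.

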14.2 Assessments during radiotherapy

Patient and clinician reported toxicity assessment at the end of each second week of treatment.

Note: This will be one assessment for those receiving 10 fractions, 2 assessments for those receiving 20 fractions and 3 assessments for those receiving 30 fractions

QoL questionnaires EQ-5D-5L, EORTC QLQ30, SCI, and health utilization at the end of radiotherapy treatment. Patients in the comparator arm will be asked to return QoL questionnaires at 7 weeks post randomisation +/- 3 weeks.

Toxicity assessment / AEs		x		x	x	x	x	x	x		x		x		x
Randomisation		x													
Pregnancy test (if applicable)		*	x												
QoL and HE Questionnaires ^{&}		x		*	*	*	x	x		x			x		x

[§]for participants randomised to receive ART

*for participants receiving 4 weeks of ART treatment

** for participants receiving 6 weeks of ART treatment

[&] EQ-5D-5L, Skin-specific Cancer Index, and EORTC QLQ-C30 , Picker Patient Experience 15 questionnaire. Please see additional table 2 for breakdown of questionnaires per hospital visit. Health Resource Utilisation should be completed in conjunction with the patient and a research nurse.

Table 2: Questionnaire administration per visit

						Time From Randomisation Date								
	Baseline	End of 2 weeks ART (for ART arm only)	End of 4 weeks ART (for ART arm only)	End of 6 weeks ART (for ART arm only)	Completion of ART (for ART arm only)	7 weeks (+/- 4 weeks) (for Non ART arm only)	4 Months	8 Months	12 Months	16 Months	20 Months	24 Months	30 Months	36 Months
EQ-5D	✓	*	*	*	✓	✓	✓	*	✓	*	*	✓	*	✓
EORTC QLQ-C30	✓	*	*	*	✓	✓	✓	*	✓	*	*	✓	*	✓
SCI	✓	*	*	*	✓	✓	✓	*	✓	*	*	✓	*	✓
PPE-15	*	*	*	*	*	*	*	*	✓	*	*	*	*	*
Patient Reported Toxicities	✓	✓	✓	✓	*	✓	✓	✓	*	✓	*	✓	*	✓
To be completed by Clinicians: Clinician Reported Toxicities	✓	✓	✓	✓	*	✓	✓	✓	*	✓	*	✓	*	✓
To be completed by research team (in conjunction with patient): Health Utilisation/ Economics	✓	*	*	*	✓	✓	✓	*	✓	*	*	✓	*	✓

Concomitant Medications	✓	*	*	*	✓	✓	✓	*	✓	*	*	✓	*	✓
-------------------------	---	---	---	---	---	---	---	---	---	---	---	---	---	---

15 Pharmacovigilance

Recording of serious adverse events (SAEs) must start from the time of randomisation and must be performed at least until 4 months after randomisation (or until 30 days following the last fraction of radiotherapy if later).

The Principal Investigator is responsible for ensuring that all site staff involved in this trial are familiar with the content of this section.

All SAEs must be reported immediately (and within 24 hours of knowledge of the event) by the PI at the participating site to the CTR PV and Safety Specialist unless the SAE is specified as not requiring immediate reporting (see section 15.2).

15.1 Definitions

Table 3. SAE definitions

Term	Definition
Adverse Event (AE)	Any untoward medical occurrence in a participant or clinical trial participant administered a medicinal product and which are not necessarily caused by or related to that product.
Adverse Reaction (AR)	Any untoward and unintended response in a clinical trial participant to radiotherapy which is related to any dose administered to that participant.
Serious Adverse Event (SAE)	Any adverse event that - 
 • Results in death. • Is life-threatening*. • Required hospitalisation or prolongation of existing hospitalisation**. • Results in persistent or significant disability or incapacity. • Consists of a congenital anomaly or birth defect. • Other medically important condition***. Please see section 15.2 for exceptions
Serious Adverse Reactions (SARs)	Any SAE occurring in a clinical trial participant for which there is a reasonable possibility that it is related to Radiotherapy at any dose administered.

Suspected Unexpected Serious Adverse Reactions (SUSARs)	A SAR, the nature and severity of which is not consistent with the Reference Safety Information table in Section 15.3.
--	--

***Note:** The term ‘life-threatening’ in the definition of serious refers to an event in which the trial participant was at risk of death at the time of the event, or it is suspected that used or continued used of the product would result in the subjects death; it does not refer to an event which hypothetically might have caused death if it were more severe.

**** Note:** Hospitalisation is defined as an inpatient admission, regardless of the length of stay, even if the hospitalisation is a precautionary measure for continued observation. Pre-planned hospitalisation e.g., for pre-existing conditions which have not worsened, or elective procedures, does not constitute an SAE.

***** Note:** other events that may not result in death, are not life-threatening, or do not require hospitalisation, may be considered as an SAE when, based upon appropriate medical judgement, the event may jeopardise the participant and may require medical or surgical intervention to prevent one of the outcomes listed above.

15.2 Trial Specific SAE Reporting requirements

In addition to the SAE reporting requirements defined in Table 4, for the purposes of this trial the following events will also be considered SAEs and must be captured on the SAE form and reported to the CTR with 24 hours of knowledge of the event:

- Skin graft failure.
- Infection requiring intravenous antibiotics (where infection started in area of surgery or radiotherapy), where CTCAE grade 3 or above.
- Bleeding considered related to the surgery or radiotherapy requiring hospitalisation.

For the purposes of this trial the following events will not require reporting as SAEs:

- Disease progression (unless more severe than expected in this population).
- Hospitalisation to facilitate radiotherapy delivery.

These should be completed in the participant’s notes and entered on the relevant toxicities eCRF page within a maximum of 4 weeks from the assessment date.

Pre-existing conditions should only be reported if they met the definitions for an SAE and if the condition worsens to a CTCAE grade 3 or above.

15.3 Causality

Causal relationship will be assessed for trial treatments and procedures:

Procedures: Radiotherapy

The Principal Investigator (or another delegated medically qualified doctor from the trial team) and Chief Investigator (or another medically qualified doctor from the Trial Management Group) will assess each SAE to determine the causal relationship:

Table 4. SAE relationship

Relationship	Description	Reasonable possibility that the SAE may have been caused by the radiotherapy?
Unrelated	There is no evidence of any causal relationship with the trial/intervention	No
Unlikely	There is little evidence to suggest there is a causal relationship with the trial/intervention (e.g., the event did not occur within a reasonable time after administration of the trial medication). There is another reasonable explanation for the event (e.g., the participant's clinical condition, other concomitant treatment).	No
Possible	There is some evidence to suggest a causal relationship with the trial/intervention (e.g., because the event occurs within a reasonable time after administration of the trial medication). However, the influence of other factors may have contributed to the event (e.g., the participant's clinical condition, other concomitant treatments).	Yes
Probable	There is evidence to suggest a causal relationship and the influence of other factors is unlikely.	Yes
Definite	There is clear evidence to suggest a causal relationship and other possible contributing factors can be ruled out.	Yes

The causality assessment given by the Principal Investigator (or delegate) cannot be downgraded by the Chief Investigator (or delegate), and in the case of disagreement both opinions will be provided.

